### 5.1.2 Study Diagram

The trial design is depicted in [Figure 1](#).

Figure 1 Study Diagram

MK-7162 in Combination with Pembrolizumab				
MK-7162 @ 25 mg QD	MK-7162 @ 50 mg QD	MK-7162 @ 100 mg QD	MK-7162 @ 200 mg QD	MK-7162 @ 400 mg QD
Pembrolizumab @ 200 mg IV Q3W	Pembrolizumab @ 200 mg IV Q3W	Pembrolizumab @ 200 mg IV Q3W	Pembrolizumab @ 200 mg IV Q3W	Pembrolizumab @ 200 mg IV Q3W

- ❖ Dose escalation and confirmation using an mTPI design based on a 6 week DLT observation period to identify a preliminary RP2D
- ❖ One 3-week treatment cycle of MK-7162 monotherapy is followed by MK-7162 combination with pembrolizumab for 35 treatment cycles (total of 36 cycles on treatment)
- ❖ MK-7162 is administered orally QD. Pembrolizumab is administered by IV infusion, and is administered on Day 1 of each 3 week treatment cycle
- ❖ Treatment of the first and second participants enrolled in each cohort will occur at least 7 days apart. Treatment of the second and third participants enrolled in each cohort will occur at least 3 days apart
- ❖ Once participants have achieved the study objectives or the study has ended, they will be discontinued from this study and may be enrolled into an extension study to continue protocol-defined assessments and treatment.

IV=intravenous; mTPI=modified toxicity probability interval; QD=once daily; Q3W=every 3 weeks; RP2D=recommended Phase 2 dose

### 5.2 Number of Participants

Approximately 40 participants will be allocated to the dose escalation and confirmation phase (Part A) of this trial. An estimated additional 150 participants will be enrolled into the dose expansion phase (Part B) of this trial.

### 5.3 Beginning and End of Study Definition

The overall trial begins when the first participant signs the informed consent form (ICF). The overall trial ends when the last participant completes the last study-related phone-call or visit, withdraws from the trial or is lost to follow-up (i.e. the participant is unable to be contacted by the investigator).

Upon study completion, participants are discontinued and may be enrolled in a pembrolizumab extension study.

### **5.3.1 Clinical Criteria for Early Trial Termination**

Early trial termination will be the result of the criteria specified below:

1. Incidence or severity of adverse drug reactions in this or other trials suggest a potential health hazard to participants
2. Plans to modify or discontinue the development of the trial drug
3. Poor adherence to protocol and regulatory requirements
4. Quality or quantity of data recording is inaccurate or incomplete

Ample notification will be provided in the event of Sponsor decision to no longer supply MK-7162 and/or pembrolizumab.

### **5.4 Scientific Rationale for Study Design**

This Phase 1b study is being conducted to evaluate the safety, tolerability, and efficacy of MK-7162 in individuals with solid tumors when administered in combination with pembrolizumab. In the dose expansion phase of this trial, which will be detailed in a future protocol amendment, MK-7162 will be administered with pembrolizumab as dual therapy or in combination with additional chemotherapeutic or immune-modulatory agents.

This study is being conducted in male and female participants at least 18 years of age with advanced solid tumors.

The precise timing of clinical/laboratory safety evaluations and/or efficacy evaluations currently outlined in the protocol may be modified during the study based on newly available MK-7162 clinical and/or preclinical safety, tolerability, or efficacy data. Additional visits may be required if changes are made to the PK/PD sampling scheme. Other modifications to the dosing and/or clinical procedures currently outlined in the protocol may be required to achieve the scientific goals of the study objectives and/or to ensure appropriate safety monitoring of the study participants.

#### **5.4.1 Rationale for Endpoints**

##### **5.4.1.1 Efficacy Endpoints**

A secondary objective for this trial is to evaluate the antitumor activity of MK-7162 in combination with pembrolizumab in participants with advanced or metastatic solid tumors. Tumor response in participants with solid tumors will be assessed by investigator using RECIST 1.1 and iRECIST. A central imaging vendor will also be used to collect, clean, and hold tumor imaging and medical photography for possible analysis by blinded, independent central review.

Sites are encouraged to have a multidisciplinary assessment plan to determine in advance which lesions will be biopsied and/or targeted for tumor assessment. If feasible, biopsied tumors should not be used for assessment by RECIST 1.1/iRECIST.

#### **5.4.1.1.1 Response Rate Assessed by RECIST version 1.1**

RECIST 1.1 will be used to determine the objective response.

#### **5.4.1.1.2 Response Rate Assessed by Immune-based RECIST (iRECIST)**

RECIST 1.1 has been adapted to account for the unique tumor response characteristics seen following treatment with immunotherapeutic agents (Section 9.2.5). Immunotherapeutic agents may produce antitumor effects by potentiating endogenous cancer-specific immune responses. The response patterns seen with such an approach may extend beyond the typical time course of responses seen with cytotoxic agents and may manifest a clinical response after an initial increase in tumor burden or even the appearance of new lesions. Thus, standard RECIST 1.1 may not provide an accurate response assessment to immunotherapeutic agents. Based on an analysis of participants with melanoma enrolled in KEYNOTE-001 (KN001), 7% of evaluable participants experienced tumor pseudo-progression. Of note, participants who had progressive disease (PD) by RECIST 1.1 but not by the immune-related response criteria [Wolchok, J. D., et al 2009] had longer overall survival than participants with PD by both criteria [Hodi, F. S., et al 2014]. Additionally, the data suggest that RECIST 1.1 may underestimate the benefit of pembrolizumab in approximately 10% of participants. These findings support the need to apply a modification to RECIST 1.1 that takes into account the unique patterns of atypical responses in immunotherapy and enables treatment beyond initial radiographic progression, if the participant is clinically stable.

Modified RECIST 1.1 for immune-based therapeutics (iRECIST) assessment has therefore been developed and published by the RECIST Working Group, with input from leading experts from industry and academia, along with participation from the United States (US) Food and Drug Administration (FDA) and the European Medicines Agency (EMA) [Seymour, L., et al 2017]. The unidimensional measurement of target lesions, qualitative assessment of non-target lesions, and response categories are identical to those of RECIST 1.1, until progression is seen by RECIST 1.1. However, if a participant by RECIST 1.1 with progression is clinically stable, treatment may be continued until additional imaging is performed that confirms radiographic progression. iRECIST will be used by Investigators to assess tumor response and progression and make treatment decisions

For further information on iRECIST, see Section 9.2.5.

#### **5.4.1.2 Safety Endpoints**

The primary objective of this trial is to characterize the safety and tolerability of MK-7162 in participants with advanced/ metastatic solid tumors when administered in combination with pembrolizumab. The primary safety analysis will be based on participants who experience toxicities as defined by CTCAE Version 4.0 criteria. Safety will be assessed by quantifying the toxicities and grades of toxicities experienced by participants who have received MK-7162 as monotherapy and in combination with pembrolizumab.

Safety parameters commonly used for evaluating investigational systemic anti-cancer treatments are included as safety endpoints for the study including, but not limited to, the incidence of, causality to, and outcome of AEs/SAEs; changes in vital signs and laboratory values.

### **5.4.1.3 Pharmacokinetic Endpoints**

A secondary objective of this study is to characterize the PK profile of MK-7162 following administration as a single agent and to characterize the PK profiles of MK-7162 and pembrolizumab following administration as combination therapy. The concentrations of these agents will serve as the primary readout for the PK, and these data will be used to derive PK parameters of the agents when administered alone and in combination. Furthermore, the results of these analyses will be used in conjunction with the PD, safety, and exploratory endpoint data to help assess future dosing strategies for MK-7162.

### **5.4.1.4 Pharmacodynamic Endpoints**

#### **5.4.1.4.1 Kynurenone (KYN):Tryptophan (TRP)**

The ratio of KYN to TRP will be measured in both plasma and in tumor biopsy specimens as a downstream PD marker of target engagement.

##### **5.4.1.4.1.1 Target Engagement**

An assay directly assessing target engagement will not be utilized and has therefore not been developed. Target engagement will be indirectly inferred by the KYN:TRP PD biomarker assay results.

### **5.4.1.5 Anti-Drug Antibodies (ADA)**

Anti-pembrolizumab ADA response will be determined to understand drug metabolism, exposure, and safety. Formation of ADAs can potentially confound drug exposures at therapeutic doses and prime for subsequent infusion-related toxicity. ADA response at the beginning of each specified treatment cycle will be determined to understand drug metabolism, exposure, and safety. The incidence of antidrug antibodies and neutralizing antidrug antibodies will be evaluated and summarized over time by dose. Correlations between the presence/absence of positivity for antidrug antibodies and PK and PD markers, activity, and safety will be explored.

### **5.4.1.6 Planned Exploratory Biomarker Research**

In addition to the specified analyses, exploratory analyses of metabolite profiles may be conducted in plasma and/or serum.

#### **5.4.1.6.1 Germline Genetic Analyses**

Germline (blood) genetic analyses (eg, single nucleotide polymorphism analyses, whole exome sequencing, whole genome sequencing): This research may evaluate whether genetic variation within a clinical trial population correlates with response to the treatment(s) under evaluation. If genetic variation is found to predict efficacy or AEs, the data might inform optimal use of therapies in the patient population. Furthermore, it is important to evaluate germline deoxyribonucleic acid (DNA) variation across the genome in order to interpret tumor-specific DNA mutations. Finally, microsatellite instability (MSI) may be evaluated as this is an important biomarker of response to immunotherapy with pembrolizumab.

#### **5.4.1.6.2 Tumor Genetic Analyses**

Genetic (DNA) analyses from tumor: The application of new technologies, such as next generation sequencing, has provided scientists the opportunity to identify tumor-specific DNA changes (ie, mutations, methylation status, microsatellite instability). Key molecular changes of interest to immune-oncology drug development include (for example) the mutational burden of tumors and the clonality of T-cells in the tumor microenvironment. Increased mutational burden (sometimes referred to as a ‘hyper-mutated’ state) may generate neo-antigen presentation in the tumor microenvironment. To conduct this type of research, it is important to identify tumor-specific mutations that occur across all genes in the tumor genome. Thus, genome-wide approaches may be used for this effort. Note that in order to understand tumor-specific mutations, it is necessary to compare the tumor genome with the germline genome. MSI may also be evaluated as this is an important biomarker of response to immunotherapy with pembrolizumab.

#### **5.4.1.6.3 Tumor and Blood Ribonucleic Acid Analyses**

Tumor and blood ribonucleic acid (RNA) analyses: Both genome-wide and targeted messenger RNA (mRNA) expression profiling and sequencing in tumor tissue and in blood may be performed to define gene signatures that correlate to clinical response to treatment with pembrolizumab or other immunotherapies. Pembrolizumab induces a response in tumors that likely reflects an inflamed/immune phenotype. Specific immune-related gene sets (ie, those capturing interferon-gamma transcriptional pathways) may be evaluated and new signatures may be identified. Individual genes related to the immune system may also be evaluated (eg, IL-10). MicroRNA profiling may also be pursued.

#### **5.4.1.6.4 Proteomic Biomarkers and Immunohistochemistry (IHC)**

Proteomics and immunohistochemistry (IHC) using blood or tumor: Tumor and blood samples from this study may undergo proteomic analyses (eg, PD-L1 IHC). PD-L1 protein level in tumor sections, assessed by IHC, has been shown to correlate with response to pembrolizumab in patients with NSCLC, and an in vitro diagnostic (IVD) has been developed for use with pembrolizumab in NSCLC. Preliminary data indicates that this association may also be true in additional cancer types (eg, triple-negative breast cancer [TNBC], head and neck squamous cell carcinoma [HNSCC], and gastric cancer). Additional tumor or blood-derived proteins may also correlate with response to pembrolizumab. Therefore, tumor tissue may be subjected to proteomic analyses using a variety of platforms that could include, but are not limited to, immunoassays and liquid chromatography/mass spectrometry. This approach may identify novel protein biomarkers that could aid in patient selection for MK-7162 and pembrolizumab (MK-3475) therapy.

#### **5.4.1.6.5 Peripheral Blood Mononuclear Cell (PBMC) Phenotypic Analysis**

Phenotypic characterization and enumeration of immune suppressive cells (eg, myeloid-derived suppressor cells [MDSC], regulatory T cells [Treg]) and activated/proliferating T-cell subsets (eg, Ki67, human leukocyte antigen – antigen D related [HLA-DR]) circulating in blood collected at pre- and post- treatment time points may be assessed by flow cytometry as a potential PD biomarker downstream of target engagement.

#### 5.4.1.6.6 Other Blood-derived Biomarkers

Other blood derived biomarkers: In addition to expression on the tumor tissue, PD-L1 and other tumor-derived proteins can be shed from tumor and released into the blood. Assays such as enzyme-linked immunoassay can measure such proteins in serum. Correlation of expression with response to pembrolizumab therapy may identify new approaches for predictive biomarkers in blood, representing a major advance from today's reliance on assessing tumor-based biomarkers. This research would serve to develop such assays for future clinical use.

#### 5.4.1.7 Future Biomedical Research

The Sponsor will conduct Future Biomedical Research on specimens consented for future biomedical research during this clinical trial. This research may include genetic analyses (DNA), gene expression profiling (RNA), proteomics, metabolomics (serum, plasma) and/or the measurement of other analytes, depending on which specimens are consented for future biomedical research.

Such research is for biomarker testing to address emergent questions not described elsewhere in the protocol (as part of the main trial) and will only be conducted on specimens from appropriately consented participants. The objective of collecting/retaining specimens for Future Biomedical Research is to explore and identify biomarkers that inform the scientific understanding of diseases and/or their therapeutic treatments. The overarching goal is to use such information to develop safer, more effective drugs/vaccines, and/or to ensure that participants receive the correct dose of the correct drug/vaccine at the correct time. The details of this Future Biomedical Research sub-trial are presented in Appendix 6 – Collection and Management of Specimens for Future Biomedical Research.

### 5.5 Justification for Dose

#### 5.5.1 Rationale for Starting and Maximum Dose of MK-7162

While the mechanism of IDO1 inhibition by MK-7162 is distinct from that of epacadostat, due to the common molecular target, there may be effects common to both. In published results of early clinical trials, epacadostat has been associated with common adverse effects (>20%) of fatigue, nausea, decreased appetite, and vomiting, constipation, abdominal pain, diarrhea, dyspnea, back pain, and cough. Two dose-limiting toxicities were observed, radiation pneumonitis and fatigue, both of which were grade 3 and were determined to be possibly related to therapy. This includes the following: one DLT occurred at the dose of 300 mg BID (grade 3, radiation pneumonitis); another DLT occurred at 400 mg BID (grade 3, fatigue).

Treatment with epacadostat produced significant dose-dependent reductions in plasma KYN levels and in the plasma KYN:TRP ratio at all doses and in all patients. Epacadostat doses of 100 mg BID achieved >80% to 90% inhibition of IDO1 at peak and 50% inhibition at trough. Although no objective responses were detected, stable disease lasting greater than or equal to 16 weeks was observed in 7 of 52 patients [Beatty, G. L., et al 2017]. Grade 3 AST/ALT elevation was observed in 1 patient but was attributed to biliary duct obstruction consistent with progressive disease. A second patient also experienced grade 3 AST/ALT elevations, but this was determined to be most likely related to acetaminophen ingestion over the maximum recommended daily dose for tumor-related fevers.

[REDACTED]

The

NHV study assessed a starting MK-7162 dose of 3 mg, which was based on the no-observed adverse effect level (NOAEL) determined in nonclinical safety studies performed in the most sensitive and relevant animal species, adjusted with allometric factors to calculate the Human Equivalent Dose (HED), reduced by appropriate safety factors according to the particular aspects of the molecule and the design of the clinical trials. The maximum dose selected for the NHV study is currently 300 mg, based on the exposures at the NOAEL dose level in the preclinical species of rat and dog, and was projected to have an exposure lower than the NOAEL exposure of either preclinical species. The analysis of clinical PK data from the NHV SAD study has been reviewed alongside safety and tolerability data. The PK data in normal healthy participants over the dose range of 3 to 300 mg will continue to inform the dosing range for this study.

Based on data from in vitro experimentation, animal models, and human experience with other inhibitors of IDO1, MK-7162 is expected to have broad clinical efficacy against a variety of tumor types when used in conjunction with pembrolizumab. [REDACTED]

[REDACTED] Prior studies of IDO1 inhibition in cancer patients have shown that this level of IDO1 inhibition is well tolerated, and preliminary studies suggest that there may be enhancement of the anti-tumor response with PD-1/PD-L1 blockade at this level of IDO1 inhibition.

[REDACTED]

This dose was found to be both safe and well tolerated when administered as a single dose to normal healthy participants. Therefore, an MK-7162 dose of 25 mg PO QD will be the starting dose for the dose escalation and confirmation phase (Part A) of this Phase 1b trial.

### 5.5.2 Maximum Dose of MK-7162

The determination of a preliminary RP2D for MK-7162 is a primary objective for this study. This study will evaluate the following dose levels: 25 mg PO QD, 50 mg PO QD, 100 mg PO QD, 200 mg, and 400 mg PO QD. [REDACTED]

Corresponding IDO1 inhibition

in tumor cells at the tested dose levels will be evaluated using the KYN:TRP PD biomarker and fresh tumor biopsy specimens.

cc1  
[REDACTED]

.

### **5.5.3 Rationale for Dose Interval and Escalation Increments**

The starting dose and dosing interval in participants of the MK-7162 Phase 1b study are based on an integration of clinical, nonclinical, toxicological, PK, and PD data. Dose finding will proceed with a model-based dose mTPI approach with a minimum of 3 participants treated per dose level: 25 mg QD, 50 mg QD, 100 mg QD, 200 mg, and 400 mg QD.

#### **5.5.3.1 Dose Finding Using a Modified Toxicity Probability Interval Design**

The mTPI design [Ji Y, Li Y, Bekele BN 2007] of this study will target a DLT rate of 30%. The starting dose for the mTPI will be MK-7162 25 mg QD. Dose escalation and de-escalation decisions are based on the mTPI design and depend on the number of participants enrolled and number of DLTs observed at the current dose level.

A minimum of 3 participants are required at each dose. However, depending on the accrual rate and the occurrence of DLTs, 3, 4, 5, or 6 participants may be enrolled at each new dose level. In [Table 1], the columns indicate the numbers of participants treated at the current dose level, and the rows indicate the numbers of participants experiencing DLT. The entries of the table are the dose-finding decisions: E, S, D, and DU represent escalating the dose, staying at the same dose, de-escalating the dose, and excluding the dose from the trial due to unacceptable toxicity, respectively. For example, if 0 out of 3 participants at a given dose level develop a DLT, then the dose can escalate to the next level. If 2 participants out of 3 develop a DLT, the dose will be de-escalated to the next lower dose level. If 3 out of 3 participants develop a DLT, this indicates an unacceptable toxicity at this dose. The dose should be de-escalated and the current dose will not be explored further. If 1 out of 3 participants at a given dose level develops a DLT, then additional participants should be enrolled at that dose level following the rules below.

When adding participants to a dose level in response to a “stay” decision, the same principles will be applied whether 3, 4, 5, or 6 participants are initially enrolled at that dose level. First, the number of additional participants to be enrolled is capped to minimize the exposure to a dose that may be unacceptably toxic (denoted as DU in [Table 1]). Secondly, to determine how many more participants can be enrolled at the dose level, one can count steps in diagonal direction (down and to the right) from the current cell to the first cell marked DU. For example, if 1 of 3 participants have experienced a DLT at a given dose level, no more than an additional 3 participants should be enrolled at this dose level until additional DLT data are available. This is because this dose level would be considered unacceptably toxic if all 3 of the additional participants experience a DLT (ie, 4/6 participants with DLT in [Table 1]).

A D or DU decision at the lowest dose level will stop the trial. An E decision at the highest dose level will result in staying at that level. During dose finding, it may be acceptable to de-escalate to an intermediate dose that was not predefined and not previously studied if evaluation of toxicity at such a dose is desired. If this approach is taken, 3 to 6 new participants may be enrolled at the new intermediate dose, and the aforementioned rules should be used to determine further enrollment at this dose level.

Dose finding will end after 14 participants have been enrolled at any of the tested doses (including intermediate doses). In the event the dose-finding decision is not to stay at the current dose based on the 14 participants, the dose may be escalated or de-escalated and additional participants may be treated.

The pool-adjacent-violators-algorithm [Ji, Y. and Wang, S.-J. 2013] will be used to estimate the DLT rates across doses. The dose with an estimated DLT rate closest to 30% will be treated as a preliminary MTD. The final RP2D for future studies will be based on all available safety and tolerability assessments from the Dose Escalation and Confirmation Phase, Dose Expansion Phase, as well as PK and PD data, and preliminary efficacy assessments from this trial.

Note that although 30% was the target toxicity rate used to generate the guidelines in [\[Table 1\]](#), the observed rates of participants with DLTs at the MTD may be slightly above or below 30%.

Table 1 Dose-finding Rules per mTPI Design

Number of participants with at least 1 DLT	Number of Participants Evaluable for DLT at Current Dose											
	3	4	5	6	7	8	9	10	11	12	13	14
0	E	E	E	E	E	E	E	E	E	E	E	E
1	S	S	S	E	E	E	E	E	E	E	E	E
2	D	S	S	S	S	S	S	E	E	E	E	E
3	DU	DU	D	S	S	S	S	S	S	S	S	S
4		DU	DU	DU	D	D	S	S	S	S	S	S
5			DU	DU	DU	DU	DU	D	S	S	S	S
6				DU	DU	DU	DU	DU	D	S	S	S
7					DU	D						
8						DU						
9							DU	DU	DU	DU	DU	DU
10								DU	DU	DU	DU	DU
11									DU	DU	DU	DU
12										DU	DU	DU
13											DU	DU
14												DU

DLT = Dose limiting toxicity; D = De-escalate to the next lower dose; DU = The current dose is unacceptably toxic; E = Escalate to the next higher dose; S = Stay at the current dose.

Target toxicity rate = 30%

Flat noninformative prior Beta (1,1) is used as a prior and  $\epsilon_1=\epsilon_2=0.03$  [Ji Y, Li Y, Bekele BN 2007], [Ji, Y., et al 2007], [Ji, Y. and Wang, S.-J. 2013]

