An mTPI design [Ji, Y. and Wang, S.-J. 2013] will be used to identify and confirm the RP2D of MK-7162 in combination with pembrolizumab. Participants will initially be enrolled in the first dose-level cohort, receiving MK-7162 monotherapy for Cycle 1, and then receiving MK-7162 in combination with pembrolizumab for subsequent cycles (Cycles 2 to Cycle 36). Lower and/or higher doses of MK-7162 may then be explored depending on the combined safety, PK, PD, and preliminary efficacy data available at each dose level. The dose of pembrolizumab will remain constant at 200 mg IV Q3W.

The final number of participants enrolled will depend on the DLT observations and what dose is ultimately identified as the RP2D using the mTPI design. For the purposes of dose escalation decisions from a safety perspective, participants will be considered evaluable for DLT if they have completed the 6-week DLT evaluation period (completed the first and second cycles or discontinued treatment due to a DLT).

Dose finding and confirmation in Part A of the trial will end after 14 participants have been treated at any of the selected doses (which may include optional doses). In the event the dose-finding decision is not to stay at the current dose based on the 14 participants, the dose may be escalated or de-escalated and additional participants may be treated. The pool-adjacent-violators algorithm [Ji, Y. and Wang, S.-J. 2013] will be used to estimate the DLT rates under the assumption of monotonicity between DLT rates and dose levels. The dose with an estimated DLT rate closest to 30% may be treated as a preliminary RP2D. The totality of the data will be considered before deciding on the dose(s) to carry forward to Part B (dose expansion).

The primary objective is to identify the RP2D of MK-7162 for use in combination with pembrolizumab. The preliminary RP2D may be the same as the MTD/MAD, or the preliminary RP2D may be selected based on overall exposure, emerging safety and tolerability data, PK data, PD data, and preliminary clinical benefit data from this study.

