### **10.6.2 Statistical Methods for Safety Analysis**

Safety and tolerability will be assessed by clinical review of all relevant parameters including AEs, SAEs, deaths, laboratory tests, VS, ECG measurements, and physical examinations.

Adverse events will be summarized by counts and frequencies for each dose level.

Laboratory tests, VS, and other safety endpoints will be summarized as appropriate.

Dose limiting toxicities will be listed and summarized by dose level. The pool adjacent-violators-algorithm [Ji Y, Li Y, Bekele BN 2007], which forces the DLT rate estimates to be non-decreasing with increasing dose levels and pools adjacent violators for weighted estimates by sample size, will be used to estimate the DLT rates across doses. The estimate of the DLT rates among participants treated at the MTDs (or MADs) and the 80% Bayesian credible interval based on a prior distribution of Beta (1,1) for the estimate will be provided.

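### The rule naming the preliminary MTD is not limited to doses that Table 1 leaves in the trial, so in a rare outcome it names a dose excluded as DU

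*Combined protocol and SAP*

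**What the plan says.** Section 5.5.3.1 sets a 30% target DLT rate and gives the dose-finding decisions in Table 1. DU is described as "excluding the dose from the trial due to unacceptable toxicity", and the 3/3 example adds that such a dose is not explored further. Dose finding ends once 14 participants are enrolled at a dose. If the decision at that point is something other than stay, "the dose may be escalated or de-escalated and additional participants may be treated".

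DLT rates are then estimated across doses by the pool-adjacent-violators algorithm, and "The dose with an estimated DLT rate closest to 30% will be treated as a preliminary MTD". A note adds that "the observed rates of participants with DLTs at the MTD may be slightly above or below 30" per cent.

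Section 5.1.1 has a softer parallel: "The dose with an estimated DLT rate closest to 30% may be treated as a preliminary RP2D". There the totality of the data is considered before doses go forward to Part B.

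Section 10.6.2 says that the algorithm "pools adjacent violators for weighted estimates by sample size". It also promises "The estimate of the DLT rates among participants treated at the MTDs (or MADs) and the 80% Bayesian credible interval", based on a Beta(1,1) prior. Neither section says whether the quantities pooled are raw rates or posterior means.

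**The concern.** The exclusion rule and the selection rule sit in the same section but are not connected. The stated consequences of DU concern dosing. The selection sentence is mandatory in form and ranges over all estimated doses. A nearest-to-target rule is symmetric, so a dose well above 30% can beat a dose at 0%.

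If that happens, the dose reported as the preliminary MTD is one the design has declared unacceptably toxic, and the interval reported for the MTD belongs to that dose. The preliminary MTD is a prespecified output tied to the primary objective, so the rule should not be able to return an excluded dose.

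**Working it through.** **Inputs.** Target 0.30, the Beta(1,1) prior and the Table 1 cells come from Section 5.5.3.1; the interval method comes from Section 10.6.2. Section 10.9's scenario without DLTs reproduces: 4×3 + 14 = 26. It confirms that the last dose is filled to 14.

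**A reachable path on legible cells.**
- Lower dose: 0/3 (E).
- Next dose: 1/3 (S), 2/6 (S), 5/9 (DU). The diagonal count from 2/6 runs 3/7, 4/8, 5/9, so three more participants are allowed.
- Back at the lower dose, enrolment continues to 0/14. With two doses this uses 9 + 14 = 23 participants.

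**Selection on raw rates.** The rates 0 and 5/9 are already ordered, so nothing is pooled.
- Excluded dose: |5/9 − 0.30| = 0.556 − 0.300 = 0.256.
- Lower dose: |0/14 − 0.30| = 0.300.

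The excluded dose is nearer and is named.

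**Reported interval.** 5/9 with Beta(1,1) gives Beta(6,5). The 80% interval is 0.354 to 0.733, and P(rate > 0.30) = 0.953.

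**How narrow the condition is.**
- One DLT in 14 below removes it: |1/14 − 0.30| = 0.229 < 0.256.
- Among legible DU cells only 5/9 is nearer than 30 points; 6/10 is exactly 0.300 away.
- With posterior means, 5/9 becomes 6/11 = 0.545 (distance 0.245) and 0/14 becomes 1/16 = 0.0625 (distance 0.2375), so the lower dose wins. With three further doses at 0/3 (posterior mean 0.20) pooled in, the lower estimate is (9×0.20 + 14×0.0625)/23 = 0.116, distance 0.184, and again there is no reversal.

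**Frequency.** The documents give no operating characteristics, so the DLT curves are assumptions. There were 40,000 trials per curve with cohorts of 3, raw rates, printed cells, and stopping at 14. The cells 7/12, 7/13, 7/14 and 8/14, which cannot be read reliably in the available text, were taken as D. Doses above a DU dose counted as excluded, and E into an excluded dose meant staying.

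| Assumed curves (DLT %, five doses) | Excluded dose named |
|---|---|
| Smooth: 5/10/20/30/45, 5/10/15/25/40, 2/5/10/20/35, 10/20/30/45/60 | about 0.2–0.4% |
| Steep: 1/2/3/50/70 | 5.66% |
| Steep: 1/2/3/5/50 | 3.85% |
| Steep: 2/3/5/45/60 | 3.46% |

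Almost all of the steep-curve results are the 5/9 outcome (5.65%, 3.85%, 3.44%). If an intermediate dose is always tried after the first DU, with an assumed rate midway, the steep figures fall to 0.56–0.97% and the smooth ones to 0.05–0.13%.

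**Sensitivity to the cap.** Section 5.5.3.1 words the cap for additions after a stay decision. The tabulated figures match a simulation that also applies it when a dose is re-entered after D, which opens routes such as 3/6, 4/8 (D), 5/9. On 1/2/3/50/70 the direct S, S, DU route alone has probability 0.375 × 0.375 × 0.125 = 1.76% at the fourth dose. Multiplied by 0.97^14 = 0.653 for 0/14 below, this is about 1.1%. A check run of 20,000 trials per curve with the cap on stay decisions only gave about 1.2–1.7% on the steep curves and about 0.1% on the smooth ones.

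**The case against.** The strongest reply is that a dose labelled unacceptably toxic cannot sensibly be called the maximum tolerated dose, and that the note on observed rates at the MTD shows this intent. As a reading of intent that is probably right. It does not limit the selection sentence, which is mandatory and has no candidate set.

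A second reply is that the example depends on raw rates, which the documents do not specify. That stands. Weighting by sample size describes the pooling and fits either estimator.

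A third is that 0/14 is an E decision, so dosing could go on. That also stands as a condition: Section 5.5.3.1 permits further treatment there but does not require it.

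A reader might infer that an excluded dose would be given again or carried into Part B. The documents do not support this. An excluded dose is not explored further, the final RP2D uses all available data, Section 5.1.1 says may and invokes the totality of the data, and Part B needs an amendment. DLTs are also listed by dose level, so 5/9 would be visible.

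A reader might also blame the absence of a tie rule. No tie is involved in the example: 0.256 is strictly smaller than 0.300. Ties are a separate matter of detail, largely covered by the provision for an MTD or MAD.

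**Conclusion.** The gap is real and narrow. As written, the Section 5.5.3.1 sentence can name a dose that the same section has excluded, and Section 10.6.2 would attach that dose's interval to the MTD label. This requires raw rates, a stop at 14, and no DLTs in 14 at the dose below.

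On the assumed curves it happens in well under 1% of trials when toxicity rises gradually, and in about 3.5 to 6% when it jumps sharply. The upper figures depend on how the cap is applied on re-entry and on no intermediate dose being used; other readings bring them to about 2% or less. The consequence is confined to the preliminary label and its reported interval. It merits a wording correction and does not call the design into question.

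**What to change.** Reconcile the DU definition and the selection sentence in Section 5.5.3.1, and the parallel sentence in Section 5.1.1. Keep pool-adjacent-violators estimation on all tested doses, which respects "under the assumption of monotonicity between DLT rates and dose levels", but apply the nearest-to-30% selection only to doses the design has not excluded as DU. In the example this leaves the 0/14 dose as the only candidate.

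The sponsor should also state, in Sections 5.5.3.1 and 10.6.2, which estimator is pooled. This review does not prescribe raw rates or posterior means.

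The cost is one clause in each of Sections 5.5.3.1 and 5.1.1 and a few words in Section 10.6.2. Sample size, dosing and visits are unaffected.
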